Primary outcome measure: comparison between groups of the percentage of area in which the disclosing plaque agent is present (RPA: Residual Plaque Area).

RPA: residual plaque area: percentage of area with residual plaque coloured by disclosing plaque agent. This will be calculated with a ImageJ Software.

Secondary outcome measure:

- comparison between groups of FMPS (Full Mouth Plaque Score) after professional oral hygiene – clinical parameter
- comparison between groups on execution time
- comparison between groups about feeling of patient ad operator

STUDY POPULATION

One hundred and twenty (120) children, aged 6-12 years, will be entered into study (randomized). It is expected that forty (120) subjects will complete the study.

Randomized subjects who deviate from the protocol (major protocol deviation) and, for this reason, are excluded from the analysis, will be replaced to guarantee that the sample required for the analysis (120) is reached.

Patient will be treated at the Department of Surgical Specialities Radiological Science and Public Health, School of Dentistry, Section of Periodontics, Brescia, Italy from 01/2023.

Inclusion Characteristics

- Signed Informed Consent Form (pediatric patient and parent).
- Male and female subjects, aged 6 -12 years, inclusive.
- Good general health (ASA I e II)
- With at least 80% of dental formula
- With at least 8/12 frontal dental elements.

Exclusion Characteristics

- Not willing to follow the agreed protocol.
- Presence of orthodontic appliances.
- Tumors or significant pathology of the soft or hard tissues of the oral cavity.
- Current radiotherapy or chemotherapy.
- History of allergy to Erythritol.
- History of adverse reactions to lactose or fermented milk products.

A written informed consent will be obtained from each included patient after explanation of the risks and benefits of participating to this study. No change in the trial design will be made after approval of the Ethical Committee.

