1. STUDY DESIGN

The study design was chosen according to the current standards required by GCP and according to national requirements.

- a. A 2 by 2 parallel design.
- b. The RCT will be run as mono-center;
- c. A total of 120 subjects will be recruited to participate in the study. It is expected that all of 120 subjects will complete the study in total;
- d. Admission into the study will be via rolling admission (estimated recruitment time: 36 months);
- e. Each subject must be pediatric patient who needs a professional oral hygiene;
- a. Each subject will follow the following treatment protocol:
 - i. - Visit (T0): consent secured; screening and entry into study; baseline data collection (FMPS), randomization into one of the four treatment arms as per the randomization protocol;

ii. - Treatment (T0): all patients will receive a full-mouth professional oral hygiene. Procedures will be performed in the following chronological sequence:

- A. Place Optragate
- B. Start the timer for the executive time
- C. According to the randomization list, patients assigned to the **GBT+** will do professional oral hygiene guided by disclosing plaque (GBT):

- Placement the disclosing plaque agent (Biofilm Discloser® (EMS Electrical Medical Systems SA, CH 1260-Nyon, Switzerland)) on the teeth and rinse with only water;
- Tissue decontamination with Air-flow (Air-flow® Prophylaxis Master EMS, Nyon Switzerland) and erythritol powder (PLUS powder® EMS, Nyon Switzerland);
- Supragingival removal biofilm with Air-flow (Air-flow® Prophylaxis Master EMS, Nyon Switzerland) and erythritol powder (PLUS powder® EMS, Nyon Switzerland);
- Subgingival removal biofilm with Air-flow (Air-flow® Prophylaxis Master EMS, Nyon Switzerland) and erythritol powder (PLUS powder® EMS, Nyon Switzerland);
- Calculus removal with piezoceramic device (Air-flow® Prophylaxis Master EMS, Nyon Switzerland), with a slim tip (PS® EMS, Nyon Switzerland);
- The treatment ends, when all the disclosing plaque has been removed;
- Stop the timer and note the executive time;
- Questionnaire patient and operator;
- Placement of the disclosing plaque agent (Biofilm Discloser® (EMS Electrical Medical Systems SA, CH 1260-Nyon, Switzerland)) on the teeth and rinse with only water;
- Note the FMPS;
- Collection of the pictures.

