D. According to the randomization list, patients assigned to the **GBT-** will receive professional oral hygiene without the guide by disclosing plaque. The treatment as same as group A without the use of disclosing plaque at the beginning.

E. According to the randomization list, patients assigned to the **US+C+** will do traditional professional oral hygiene guided by disclosing plaque:

- Placement the disclosing plaque agent (Biofilm Discloser® (EMS Electrical Medical Systems SA, CH 1260-Nyon, Switzerland)) on the teeth and rinse with only water;
- Calculus removal with piezoceramic device (Air-flow® Prophylaxis Master EMS, Nyon Switzerland), with a slim tip (PS® EMS, Nyon Switzerland);
- Supragingival and subgingival removal biofilm with rubber cup and polish;

- The treatment ends, when all the disclosing plaque has been removed;
- Stop the timer and note the executive time;
- Questionnaire for the patient and the operator;
- Placement of the disclosing plaque agent (Biofilm Discloser[®] (EMS Electrical Medical Systems SA, CH 1260-Nyon, Switzerland)) on the teeth and rinse with only water;
- Note the FMPS;
- Collection of the pictures.

- F. According to the randomization list, patients assigned to the **US+C-** will receive professional oral hygiene without the guide by disclosing plaque. The treatment as same as group C without the use of disclosing plaque at the beginning.
- G. All treatments are made by the same clinician.
- H. Data collection (FMPS): A PCP-UNC 15 periodontal probe is used on six sites per tooth (mesio-buccal, buccal, disto-buccal, mesio-lingual, lingual and disto-lingual) with a gentle probing force by the same clinician. Measurements are rounded to the nearest millimeter.
- I. Clinical assessment data will be recorded via hard copy CRFs. CRFs will be submitted to a data entry staff member for entry into the statistical database. At the conclusion of the study, such statistical database will be submitted to the statistician for the preparation of the statistical analysis and the final study report.

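### The only rule for measuring FMPS describes a length in millimetres, not a plaque score, and the supplied text gives no site criterion or denominator

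*Combined protocol and SAP*

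**What the plan says.** Under STUDY OUTCOMES, the first secondary outcome is a "comparison between groups of FMPS (Full Mouth Plaque Score) after professional oral hygiene".

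Section 1, STUDY DESIGN, places one reading at the T0 visit: "baseline data collection (FMPS), randomization into one of the four treatment arms as per the randomization protocol". It places the second after treatment. In the item C and item E lists, the disclosing agent is applied and rinsed, and FMPS is then noted.

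Item H of the same section, labelled as FMPS data collection, gives the method: "A PCP-UNC 15 periodontal probe is used on six sites per tooth", "with a gentle probing force by the same clinician", and "Measurements are rounded to the nearest millimeter".

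Section 3, PROCEDURE (Clinical Periodontal Evaluation), lists FMPS as an assessment to be entered in the CRF and adds no scoring rule. Section 4, STATISTICAL ANALYSIS, names a model only for RPA and does not mention FMPS.

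**The concern.** A plaque score records whether plaque is there, site by site, and summarises that over the mouth. It has no millimetre value to round. Probing force and rounding to whole millimetres belong to a depth or length measurement, and no such measurement is among the trial's outcomes. An examiner who follows item H to the letter collects a quantity the trial does not use and leaves out the one it needs. To obtain FMPS the examiner must depart from the written rule, and the protocol does not say how: by probe, by eye or by dye.

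At stake is whether the first secondary outcome can be interpreted and repeated. Item H also makes no distinction between the baseline and final readings, although the protocol lists a dye step before only one of them.

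**Working it through.** The protocol states no effect size, standard deviation or power for FMPS, so there is no figure of that kind to reproduce. The check consists of reading every mention of FMPS and comparing what item H produces with what a plaque score needs.

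**1. Where a rule could be.** STUDY OUTCOMES names the score and its timing. The T0 visit and the item C and E lists say when it is read. Section 3 says it is recorded. Only item H says how.

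**2. What item H supplies and omits.**
- Sites: supplied, six per tooth.
- Instrument: supplied, a periodontal probe.
- Recorded quantity: whole millimetres under probing force. This is a length.
- Criterion for plaque present or absent at a site: not given.
- Denominator and formula: not given.

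No rule turns millimetres into plaque present or absent, so the recorded quantity does not lead to the outcome.

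**3. Why the denominator matters here.** Children may enter with as little as 80% of the dental formula. With six sites per tooth throughout, a child at that limit has 0.8 times the sites of a full formula. A score over the full formula would then be 0.8 times the score over sites examined. The text does not say which is meant.

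**4. Dye at each reading.**
- Final: the item C and E lists put the disclosing agent and rinse just before FMPS. GBT- follows by reference: "The treatment as same as group A without the use of disclosing plaque at the beginning". So does US+C-: "The treatment as same as group C without the use of disclosing plaque at the beginning". Reading groups A and C as GBT+ and US+C+, only the initial dye is dropped, so all four arms are dyed at the final reading.
- Baseline: no dye step is listed, and the reading comes before randomization. Dyeing everyone then would conflict with two arms starting without disclosing agent. An undyed baseline is therefore a reasonable inference, but it is not stated.

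**5. What an undyed baseline would do.** Let B be the true baseline score, F the final score (taken as fully seen with dye), and s the share of plaque-positive sites detected without dye.
- Recorded drop within an arm: sB - F. True drop: B - F. Shortfall: (1 - s)B, which is above zero when s is below 1.
- Planned contrast between arms: mean F in one arm minus mean F in another. Neither s nor B enters.
- Contrast of recorded drops between arms: because B is read before randomization, the expected sB is the same in every arm and cancels, leaving the difference in mean F.

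The dye difference thus affects only an absolute drop within an arm. The documents give no value for s, so no size is put on it.

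**6. The one stated design figure.** The 83% power is for the interaction on RPA with 30 children per arm. A simulation with the protocol's inputs (phi = 55; means 10%, 10%, 2.9%, 1.5%; two-sided 5%) gave about 81% with values floored at 0.001, about 85% with floors of 0.0001 or 0.000001, and about 86% essentially untruncated. The stated 83% lies in that range; its own Monte Carlo error is √(0.83 × 0.17 / 1000), about 1.2 points. FMPS plays no part in it.

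**The case against.** The strongest defence is that item H is a wording slip with little practical effect. Six named sites per tooth can support a present/absent score, a probe does not rule that out, and the treatment sequence already has the examiner note FMPS just after dye and rinse. There is one centre and one treating clinician, so depths are unlikely to be entered as FMPS. The CRF, listed as Appendix 1 and not supplied, may hold a proper scoring field.

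Much of this stands. It keeps the point to a rule that is wrong and easily corrected. It does not save the rule: the millimetre instruction still contradicts the outcome, no supplied section sends the reader to the CRF for a definition of FMPS, and a correct CRF would then disagree with item H.

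Three stronger readings are tempting, and the documents support none of them.
- A reader might infer that FMPS cannot be computed at all. It could be, as a present/absent score, once the millimetre rule is removed and the missing definitions are added.
- A reader might infer that an undyed baseline biases the secondary outcome. The declared comparison is on the value after treatment, when every arm is dyed. No change-from-baseline analysis is planned, and a shared under-detection before randomization would cancel between arms.
- A reader might infer that probing dyed teeth before the pictures spoils RPA. FMPS is listed before the pictures, but nothing in the documents shows that the stained area would change, or by how much.

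**Conclusion.** Wrong as written, limited to a secondary outcome. The sole measurement rule for FMPS prescribes a length that the trial does not use, and the supplied text lacks the site criterion and denominator that a plaque score needs. The rule governs 120 baseline and 120 final readings, 240 in all if every child completes.

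The planned between-group comparison of final FMPS is not biased by the dye difference. The primary outcome is computed separately with ImageJ, and its power calculation does not depend on FMPS. If the baseline is undyed, it is not on the same scale as the final value, and a drop within an arm should not be read as absolute plaque removal.

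This rests on two assumptions: that the unsupplied CRF appendix does not override item H, and, for the remark on scale only, that no disclosing agent is on the teeth at baseline.

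**What to change.** In item H, delete the probing-force and millimetre wording and put in its place:
- FMPS = (number of sites with plaque present ÷ number of sites examined) × 100, with six sites per tooth on the teeth present.
- Final reading: a site is positive if dyed plaque is visible after the disclosing agent and rinse already in the treatment sequence.
- Baseline reading: state whether disclosing agent is on the teeth and how plaque is then called at a site. If there is none, add that baseline and final values are on different scales and that a within-arm drop is not to be read as absolute plaque removal.

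Align the CRF field with this definition. The cost is protocol and CRF wording, submitted by the amendment route in section 9. It needs no extra children, visits or devices, and it leaves the primary analysis and sample size as they are.

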2. TREATMENTS

Plus Powder and Biofilm Discloser[®] by EMS Electrical Medical Systems SA, CH 1260-Nyon, Switzerland will be delivered to the study center prior study start.

Concomitant Therapy

A necessary concomitant medication or therapy is permitted as long as it is not excluded in the exclusion criteria. Every medication has to be reported in the CRF (Appendix 1) and in the Concomitant Medication form (Appendix 2). All changes during the study are to be reported in the CRF. Usage of prohibited therapy will lead to the exclusion of the subject.

Blinding and Randomization

Blinding: The statistician will be blinded to the 4 groups identification, and defined as all the possible combination of A-b (treatment) and B-b (DPA usage).

Randomization and allocation concealment: The randomization will be done based on a computer-generated table, using a random blocks randomization algorithm, that links each patient to one of the four treatment combinations

Implementation: The Principal Investigator will be informed immediately of Serious Adverse Events (SAEs), regardless of the causality relationship between the administration of the investigational treatment and the SAE.

3. **PROCEDURE**

Screening and Selection of Subjects

Patients visiting the Department of Dentistry at Brescia University will be asked to participate in this study. Subjects will report to the clinical facility and be screened by the dental examiner to identify those subjects who meet the inclusion/exclusion characteristics. The findings of this initial screening procedure will be recorded on the CRF. Subjects who meet the inclusion/exclusion characteristics and sign an Informed Consent Form will be entered into the study.

Baseline Oral Soft and Hard Tissue Assessment

All subjects will receive an evaluation of their oral soft and hard tissues. This examination will include an evaluation of the soft and hard palate, gingival mucosa, buccal mucosa, mucogingival fold areas, tongue, sublingual and submandibular areas and the tonsillar and pharyngeal areas. The results of this evaluation will be recorded on the CRF.

Clinical Periodontal Evaluation

All patients receiving treatment will be evaluated by the dental examiner for the following assessments

- Full Mouth Plaque Score (FMPS).

All parameters will be recorded in the CRF.

Treatment

Patients who have been identified for treatment will be randomized according to a randomization table generated. The entire mouth will be treated (supra/subgingival) in a single session. If the patient has been identified to receive the control treatment, all teeth

present will not receive the application of disclosing agent and will receive directly full-mouth supragingival and intra sulcular biofilm removal with Airflow or rubber cup and full mouth calculus removal. If the patient has been identified to receive the test treatment, he/she will start full mouth with the application of disclosing plaque.

A questionnaire and OHI are administered

4. STATISTICAL ANALYSIS

Data will be described using standard summary statistics such as mean and standard deviations for quantitative variables, absolute counts and proportions for categorical variables. The primary outcome is Residual Plaque Area (RPA). RPA, expressed as proportion (0-1) will be modelled using a beta-regression model.

Results will be expressed as estimates and relative 95% confidence intervals. A significant level of 5% will be used for all the comparisons and all analysis will be performed using R (version 4.2.1 or higher).

Sample size determination

Sample size was estimated via Monte Carlo simulation (B=1000 runs). We assumed a beta-regression model for RPA with technique (USB,GBT) and DPA (No,Yes) as main factors, and their interaction. The parameter of interest is the interaction, i.e. if applying the DPA is giving better results depending on the main technique used. Using data from a previous study on RPA we estimated the phi parameter for a beta distribution (phi=55) and assumed a baseline RPA (no DPA in either techniques) of 10%, with a reduction to 2.9% and 1.5% respectively for USB+C+ and GBT+.

Through simulation we evaluated the sample size needed to achieve a power of at least 80% for the test on interaction term assuming a 5% significance level. A sample size of 30 patients in each of the four group (N=120 overall) achieved a 83% power.

Evaluation of Safety

The following safety variables will be used for the evaluation of safety:

- Adverse events (AE);
- Adverse reactions (AR).

The total number of AEs and the total number of AEs at least possibly related to the study treatment, as well as the total number of patients affected by at least one adverse event will be calculated per treatment group.

The type of AE classified by organ system (according to MedDRA terminology) will be tabulated. Serious and/or unanticipated adverse events and AEs resulting in discontinuation or reduction/withdrawal of the study treatment will be presented separately.

Safety analysis set

Safety summaries will be based on the safety analysis set which will consist of all patients who received the test/control treatment.

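### An unadjusted 5% level covers every comparison and no confirmatory test is named, so RPA claims outside the interaction carry an error rate well above 5%

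*Combined protocol and SAP*

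**What the plan says.** The analysis rule in section 4 (Statistical Analysis) is one sentence: "A significant level of 5% will be used for all the comparisons". The same paragraph names RPA as the primary outcome and beta regression as the model, and says "Results will be expressed as estimates and relative 95% confidence intervals". It names no contrast, no order of testing and no multiplicity procedure.

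Study Outcomes describes the primary outcome as follows: "Primary outcome measure: comparison between groups of the percentage of area in which the disclosing plaque agent is present". It then lists between-group comparisons of full-mouth plaque score (FMPS) and of patient and operator feeling, and a "comparison between groups on execution time". These three are labelled secondary. The Structure entry lists four parallel arms, and section 1 calls the design 2 by 2.

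The interaction of technique with DPA appears only under Sample size determination. There it is called the parameter of interest, and the simulation sought to "achieve a power of at least 80% for the test on interaction term assuming a 5% significance level". The result was: "A sample size of 30 patients in each of the four group (N=120 overall) achieved a 83% power".

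**The concern.** The sample-size paragraph says what was powered. It does not say that efficacy will be judged on that test alone, and the analysis paragraph above it applies 5% to everything. The stated objective covers both the disclosing agent and the erythritol powder, so it invites a claim about the dye and a claim about the technique as well as a claim about their interaction.

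Read as written, a headline result on the primary outcome could come from the interaction, an averaged factor effect, or any of the six pairs of arms, each judged at 5% and chosen after the data are seen. The 5% would then not be the error rate of the trial's conclusion on its own primary outcome.

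**Working it through.** **Inputs from section 4.** There are four arms of 30, with beta precision phi = 55. Mean RPA is 10% in both arms without DPA, 2.9% with ultrasonic plus DPA (US+C+) and 1.5% with GBT plus DPA (GBT+). The model has two factors and their interaction, tested at 5%. *Assumed because not stated:* logit link, two-sided tests (consistent with the 95% intervals), common phi, no dropout.

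**Step 1: the effect that was powered.** logit(p) = ln[p/(1−p)].

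- logit(0.10) = −2.197; logit(0.029) = −3.511; logit(0.015) = −4.185.
- Interaction = (−4.185 + 2.197) − (−3.511 + 2.197) = −0.674.
- Averaged technique effect = ½(0 − 0.674) = −0.337.

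**Step 2: reproduce the stated 83%.** In 20,000 simulated trials fitted by maximum likelihood, interaction power was 85.2% (Wald z), 85.0% (likelihood ratio), 84.7% (Wald t) and 83.7% (t with a small-sample-corrected standard error). The plan used 1,000 runs, so its Monte Carlo standard error is √(0.83 × 0.17/1000) = 1.2 points. Batches of 1,000 Wald-z runs ranged from 81.8% to 87.9%. The stated figure reproduces.

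**Step 3: chance of at least one false RPA claim at an unadjusted 5%.**

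| Truth | Tests | Wald z | Corrected SE |
|---|---|---|---|
| All arms equal | Six pairwise | about 22% | 19.2% |
| All arms equal | Two averaged main effects and interaction | about 16% | 13.4% |
| Only the dye works (10/2.9/10/2.9%) | Interaction, averaged technique effect, two technique effects within DPA level | about 14% (13.8–14.6%) | – |
| Dye effect present, no interaction | Interaction alone | about 5.5% | – |

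As a check on the first row, normal theory for six pairwise tests gives 20.3%. Treating the tests as independent would give 1 − 0.95⁶ = 26.5%, which is too high because the pairs share arms.

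**Step 4: interaction power at 30 per arm under different adjustments.**

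| Interaction tested | Wald z | Corrected SE |
|---|---|---|
| Alone at 5% | 85.2% | 83.7% |
| Holm with two averaged main effects | 82.4% | 80.4% |
| Holm over three treatment-coded terms | 77.8% | 75.4% |
| Holm with six pairwise tests | 76.9% | 74.4% |

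Treatment coding costs power because the technique term then becomes the technique effect without DPA. The plan assumes that effect is zero (10% against 10%), so the term is seldom rejected and the interaction must usually pass a stricter threshold.

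**Step 5: power of the follow-up contrasts if the interaction stands outside the Holm family.** Holm over the six pairwise tests gives 88.7% for GBT+ against US+C+ (87.1% with corrected standard errors) and about 100% for the four contrasts of a 10% arm with a low-RPA arm. Adding the two averaged effects makes eight tests. Those eight lie inside a nine-test family (six pairwise, two averaged, interaction) for which the corrected-SE figures are 81.9% for GBT+ against US+C+ and 72.6% for the averaged technique effect. Removing a test from a Holm family never makes it harder to reject the others, so the eight-test values are no lower than these.

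**The case against.** The strongest reply is that the plan does have one hypothesis. It calls the interaction the parameter of interest, ties both the 80% target and the 83% power to it, specifies a factorial model, and labels the other outcomes secondary. That test alone has close to 5% error. No section lists pairwise contrasts.

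All arms being equal is also far from what the plan expects. Under its own means only one of the six pairwise nulls is true (the two arms without DPA), and the false-positive chance across all six is about 5.5%. If only the dye works, two are true and it is 10.4%.

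Much of this stands. The 22% depends on a family of tests that the plan neither specifies nor excludes, and on no arm differing. What does not stand is the idea that naming a parameter under sample size limits the claims: the operative sentence in the analysis section covers every comparison, and the primary outcome is worded openly.

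Two stronger readings are tempting and are not supported:

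- A reader might compound the error over all outcomes into one trial-wide figure. That would need independence between outcomes, which is implausible because RPA and FMPS both measure residual plaque in the same child after the same dye. It would also need a number of tests per outcome that no section gives.
- A reader might infer that any Holm correction keeps the interaction above 80%. Step 4 shows that this depends on the family and the coding.

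**Conclusion.** The concern holds. Section 4 sets an unadjusted 5% for all comparisons, and the documents do not make the interaction the sole confirmatory test. With all arms equal, the chance of a false RPA claim is about 22% over six pairwise tests and about 16% over three factorial contrasts (19% and 13% with corrected standard errors). If only the dye works, it is about 14% for technique-related claims.

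These are conditional figures. They are not the trial's error rate, because the documents do not commit to either family. The interaction tested alone stays near 5%, and its stated power is sound under the plan's assumptions. The results rest on the assumptions listed with the inputs. The point should be settled before database lock.

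**What to change.** Replace the significance-level sentence in section 4 with:

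*The technique-by-DPA interaction on RPA is the single confirmatory test, two-sided 5%. The follow-up RPA contrasts (averaged DPA and technique effects, pairwise arm contrasts) are Holm-adjusted as one family and are supportive. FMPS, execution time and patient/operator feeling are reported as estimates with 95% CIs and labelled exploratory.*

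Reword the primary outcome in Study Outcomes to match.

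The cost is one paragraph, notified to the Ethical Committee as section 9 requires. No patients are added and the 83% interaction power is unchanged. The downside is lower power for the follow-up contrasts. GBT+ against US+C+ stays at about 89% under Holm over the six pairwise tests, and at no less than about 82% in the full eight-test family. The averaged technique effect could be as low as about 73%.

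If the sponsor prefers DPA, technique and interaction all to be confirmatory under Holm, the text must specify averaged (sum-to-zero) effects. Interaction power is then about 80–83%. With treatment-coded terms it falls to about 75–78%, below the plan's own target.

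### The only RPA model written out does not use baseline FMPS, which is already collected: a cheap possible gain in precision, not an error

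*Combined protocol and SAP*

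**What the plan says.** The analysis paragraph of section 4 says "RPA, expressed as proportion (0-1) will be modelled using a beta-regression model" and lists no terms. The sample-size paragraph of the same section gives them: "We assumed a beta-regression model for RPA with technique (USB,GBT) and DPA (No,Yes) as main factors, and their interaction". It names the interaction as the parameter of interest.

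The T0 visit in section 1 lists "baseline data collection (FMPS), randomization into one of the four treatment arms", in that order. Section 3 (Clinical Periodontal Evaluation) says "All patients receiving treatment will be evaluated by the dental examiner for the following assessments", names FMPS, and sends it to the CRF. RPA is described only after treatment, so FMPS is the only plaque measure listed before randomisation.

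Section 2 (Blinding and Randomization) describes allocation "using a random blocks randomization algorithm, that links each patient to one of the four treatment combinations" and names no stratification factor. Study Outcomes lists as a secondary outcome "comparison between groups of FMPS (Full Mouth Plaque Score) after professional oral hygiene", with no model and no mention of the baseline value.

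**The concern.** A plaque measure taken before randomisation is an obvious candidate to predict plaque left after cleaning. Here it is used neither in the allocation nor in the model that the plan writes out. If FMPS predicts RPA to a similar degree in all four arms, adjusting for it removes variation from the interaction estimate at no data cost. What is at stake is the width of one confidence interval and a few points of power. Bias is not at stake, because allocation is random.

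Section 4 also leaves the choice open, since its analysis sentence lists no terms. Settling it in advance removes a decision that could otherwise be taken with results in view.

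**Working it through.** **Inputs from section 4.** Mean RPA is 10% in both arms without disclosing agent (DPA), 2.9% in US+C+ and 1.5% in GBT+. phi = 55, 30 patients per arm, 5% level (taken as two-sided), stated power 83% from 1,000 simulation runs.

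**Reproducing the stated power.** The two no-DPA arms share a mean, so the interaction on the logit scale is logit(0.015) - logit(0.029) = -4.185 + 3.511 = -0.674. With phi estimated, the Fisher-information standard error is 0.227. Power is Phi(0.674/0.227 - 1.96) = Phi(1.01) = 84.3%. Simulation gives about 85%. The plan's 1,000 runs carry a Monte Carlo error of sqrt(0.83 x 0.17/1000) = 1.2 points, so 83% is reproduced.

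**Where the variance of the interaction sits.** Treating phi as known, each arm contributes 1/(30W), where W = phi^2 [psi'(mu phi) + psi'((1-mu) phi)] [mu(1-mu)]^2 and psi' is the trigamma function.

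- Each no-DPA arm: W = 5.38, contribution 0.0062
- US+C+: W = 2.11, contribution 0.0158
- GBT+: W = 1.46, contribution 0.0228

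The total is 0.0510. The DPA arms supply (0.0158 + 0.0228)/0.0510 = 76% of it. Adjustment therefore helps the interaction only if FMPS predicts RPA in the DPA arms.

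**Adding baseline FMPS.** The within-arm correlation r is an assumption. A standardised baseline score was linked to RPA by a Gaussian copula, which keeps the beta margins and phi = 55. Each setting had 20,000 runs (Monte Carlo error 0.25 points for power). The planned model uses model-based standard errors. The adjusted model uses sandwich standard errors with an n/(n-k) correction.

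| Assumed r | Planned power | Adjusted power | Change (points) |
|---|---|---|---|
| 0 in all arms | 85.0% | 84.0% | -1.0 |
| 0.2 in all arms | 85.5% | 85.7% | +0.2 |
| 0.3 in all arms | 85.7% | 87.2% | +1.5 |
| 0.4 in all arms | 85.6% | 89.1% | +3.5 |
| 0.5 in all arms | 85.6% | 91.8% | +6.2 |
| 0.3 no-DPA, 0.15 DPA | 85.2% | 85.4% | +0.2 |
| 0.5 no-DPA, 0.25 DPA | 85.4% | 87.5% | +2.1 |
| 0.3 no-DPA arms only | 85.3% | 84.5% | -0.8 |
| 0.5 no-DPA arms only | 84.9% | 84.6% | -0.3 |

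The standard deviation of the interaction estimate goes from 0.228 to 0.223 at r = 0.3 in all arms, and from 0.227 to 0.210 at r = 0.5 in all arms. It rises from 0.229 to 0.236 when r = 0.5 holds in the no-DPA arms only.

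**Type I error** (GBT+ set to 2.9%). Over the nine settings it is 5.3 to 6.0% for the planned test and 5.1 to 5.5% for the adjusted test with corrected sandwich errors. The choice of standard error matters when r = 0.5 holds in the no-DPA arms only. There the adjusted test has 6.7% with model-based errors, 6.0% with uncorrected sandwich errors and 5.4% with the correction, against 5.6% for the planned test.

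**The case against.** The strongest reply is that nothing is broken: the planned test is valid, its power target is met, and the gain rests on a number that the documents do not supply. That stands. A reader might infer from the omission that the primary test is biased or underpowered, and neither follows. Nor is adjustment ruled out: the terms come from the sample-size paragraph, and the analysis sentence is silent.

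The documents also give reasons to expect a low correlation where it matters. In the DPA arms treatment continues until the disclosed plaque is gone (section 1), so what remains need not follow what was there at the start. The two measures differ as well. For FMPS, "A PCP-UNC 15 periodontal probe is used on six sites per tooth", whereas RPA is the "percentage of area with residual plaque coloured by disclosing plaque agent", computed from images. This also stands, and it is why the six-point gain should not be taken as the expected result.

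A reader might take comfort from a model-based calculation for r = 0.5 in the no-DPA arms only, where power appears to rise from 85.0% to 87.9%. Part of that is test inflation, given the 6.7% type I error. With corrected sandwich errors the gain disappears.

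One could also apply the usual sqrt(1 - r^2) narrowing to post-treatment FMPS. The documents do not support a figure. Post-treatment FMPS is noted after disclosing, no disclosing step is listed at baseline, and no FMPS model is given.

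**Conclusion.** The point holds as a low-cost improvement. The change in interaction power is about -1 to +2 points if r is 0.3 or less, or if the correlation is absent or weaker in the DPA arms. It is about +6 points only if r is near 0.5 in all four arms. These figures rest on section 4's means and phi, the copula link, a linear FMPS term on the logit scale, and values of r that are assumed throughout. For post-treatment FMPS, adjusting for the same score at baseline is a sensible specification, but its benefit cannot be sized from the documents.

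**What to change.** Amend section 4 to state three things:

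- RPA is analysed by beta regression on technique, DPA, their interaction and baseline FMPS as a continuous covariate, with sandwich standard errors and the n/(n-k) correction.
- The unadjusted technique x DPA model is reported alongside.
- Post-treatment FMPS is adjusted for baseline FMPS.

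Do this before any outcome data are reviewed. The blind data review meeting in section 7 is too late for choosing a covariate, because it is held after the study is finished.

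The cost is a short amendment with the prior approval that section 9 requires. The Study Population section rules out design changes after ethics approval, but a covariate specifies the analysis and leaves the design as it is. No new data are needed. The statistical cost is one degree of freedom, about 1 point of power if FMPS does not predict RPA (85.0 to 84.0%), and a slightly different target. The adjusted interaction is conditional on FMPS and moves from about -0.68 to -0.70 on the logit scale at r = 0.5.
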